5.10 Specific reporting guidelines

Study Investigators should adhere to the following guidelines to ensure the quality and precision of AE reporting:

Use recognized medical terms.

Avoid the use of colloquialisms and non-standard abbreviations

If known at the time of AE reporting, a diagnosis should be reported instead of individual symptoms and signs (for example, record only “pneumonia” rather than “productive cough” and “elevated white blood cell count”).

If the reported symptoms and signs cannot be medically characterized as a single diagnosis or syndrome at the time of AE reporting, the information that is available should be reported. If a diagnosis is subsequently established, it should be reported as follow-up information as described earlier.

A cascade of clinical events (such as sequelae of an adverse event) should be identified as the primary, causative event. The cascade of events can be further described in the primary AE narrative. For example, when recording a death, the event or condition that caused or contributed to the fatal outcome should be reported as the serious adverse event. If the cause of death is unknown and cannot be determined at the time of reporting, “unknown cause of death” should be recorded as the adverse event.

Any AE potentially related to the study procedure that results in inpatient re-hospitalization or prolongs the index hospitalization (for study treatment) should be reported as a SAE. If a subject is re-hospitalized to undergo a medical or surgical procedure as a result of an AE, the event responsible for the procedure (not the procedure itself) should be reported as the SAE. For example, if a subject is re-hospitalized to undergo exploratory surgery as a result of a major bleeding event, record the major bleeding event that necessitated surgery as the SAE.

All observed or reported serious bleeding events occurring through the 365 day follow-up period, must be recorded.

Previously scheduled hospitalizations required for diagnostic or elective surgical procedures for the management of unchanged pre-existing medical conditions shall not be considered AEs.

5.11 Pregnancy

If a subject becomes pregnant within 90 days of receiving alteplase and undergoing ultrasound-accelerated catheter-directed thrombolysis, follow-up should be obtained from the medical record to determine the outcome of the pregnancy (successful live-birth, etc.). Congenital abnormalities must be reported as a SAE.

5.12 Categorization of adverse events

All AEs must be classified according to intensity or severity, relatedness, outcome, and treatment or action taken.

Intensity or severity

The following categories for intensity or severity of an AE should be used in reporting:

Mild	Awareness of a symptom or sign that does not interfere with the subject's usual activity or is transient and resolves without treatment and without sequelae
Moderate	Interferes with the subject's usual daily activities, but he or she is still able to function
Severe	Interrupts a subject's usual daily activities and generally requires medication, surgery, or other intervention for treatment

Relatedness

Each AE should be evaluated as to whether it was related to the study procedures, thrombolytic and anticoagulation drugs, or EkoSonic® Endovascular System as follows:

Definite	An AE that has a causal relationship to the drug (recombinant t-PA), anticoagulation medication, or the EkoSonic® Endovascular System
Probable	An AE that has a 'reasonable possibility' of a causal relationship to the use of recombinant t-PA, anticoagulation medication, or the EkoSonic® Endovascular System; another etiology is significantly less likely
Not related	An AE is not related to the use of recombinant t-PA, anticoagulation medication, or the EkoSonic® Endovascular System; there is no temporal relationship or a much more likely alternative etiology exists

Unknown	An AE where the relationship to the use of recombinant t-PA, anticoagulation medication, or the EkoSonic® Endovascular System cannot be determined.
----------------	---

Outcome

The clinical course of all AEs should be followed until a medical outcome is determined (resolution, stabilization, or determination that it was unrelated to study participation). The clinical outcome of all AEs should be recorded as follows:

Death	Subject expired
Recovered	Subject returned to baseline health and functional status
Not yet recovered	Subject did not recover and symptoms or sequelae persist
Recovered with sequelae	Subject did recover but continues to experience clinical sequelae from the adverse event

Treatment or action taken

AEs and SAEs will be categorized by the actions taken in response to the event:

Intervention	Surgery or other invasive procedure
Non-surgical treatment	Drug initiation, interruption, dose reduction, dose increase, or discontinuation
None	No action was taken

5.13 Expedited reporting of serious adverse events

Any AE that is considered serious must be reported to the device manufacturer, EKOS Corporation, within 24 hours of the site's knowledge of the event throughout the study via the e-mail address [REDACTED]

At the time of Sponsor notification, the Investigator shall enter into EDC as much of the information listed below as possible.

- a. Subjects demographics
- b. Pre-existing conditions
- c. The adverse event's description
- d. Date and time of AE onset
- e. Severity
- f. Treatment
- g. Results of diagnostic testing
- h. Duration of sequelae

- i. Outcome (if known)
- j. Information on suspected medications including dose, route of administration, frequency, dates, lot number, expiration date, and concomitant medications

When a SAE is reported, the device must be retained and returned to EKOS (see above for address for return devices). The EKOS representative may contact the Investigator to collect additional information on the EkoSonic® System.

When reporting a death, the primary event or condition that caused or contributed to the fatal outcome should be reported as the serious adverse event. Death would be reported as the outcome of the serious adverse event. If the cause of death is unknown at the time of reporting, report "unknown cause of death".

5.14 Safety Monitor

A safety monitor shall review and adjudicate all SAEs and bleeding events during the study. The safety monitor will determine if the AE meets the definition of serious and unexpected and shall notify the sponsor if the number or type of events is of concern.

5.15 Data Collection

All study data shall be recorded on paper or eCRFs. Images shall be provided to the core labs as described in the lab manual provided to the sites

Data gathered during the course of the study shall be entered into a secure electronic data capture (EDC) website as soon as possible and at least within 7 days of subject enrollment or follow-up visit. Instructions and training on data collection/entry shall be provided to the Investigator and their staff during site initiation. Data shall be reviewed on a periodic basis and any incomplete or inconsistent data will be requested from the Investigator.

6.0 STATISTICAL ANALYSIS

6.1. Analysis Subject Sets, Evaluable Subjects and Missing Data Handling Convention

Efficacy Evaluable Segments are defined as DVT segments from enrolled subjects which: (a) were successfully crossed and received EkoSonic® Treatment, and (b) had Villalta scores available at both Baseline and 30 days Post-EkoSonic® Treatment visit. The **Efficacy Segment Set** includes all efficacy evaluable segments and will be used for all segment specific efficacy analyses. A treated segment that received a revascularization procedure within 30 days Post-EkoSonic® Treatment will be regarded as a failure for the primary efficacy endpoint, i.e. without a ≥ 4 -point reduction in Villalta score from Baseline to 30 days Post-EkoSonic® Treatment.

Efficacy Evaluable Subjects are defined as enrolled subjects for whom at least one affected segment: (a) was successfully crossed and received EkoSonic® Treatment, and (b) had Villalta scores available at both Baseline and 30 days Post-EkoSonic® Treatment visit. The **Efficacy Subject Set** includes all efficacy evaluable subjects and will be used for all subject specific efficacy analyses such as for quality of life measures.

Safety Subject Set

Safety evaluable subjects are defined as enrolled subjects for whom the EkoSonic® Treatment was initiated, i.e. venous access attempted for catheter introduction. The **Safety Subject Set** includes all safety evaluable subjects and will be used for all safety analyses.

Missing data will not be imputed for the primary efficacy and safety analyses. However sensitivity analyses may be performed to assess the robustness of study results with respect to missing data.

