6.2. Statistical Analysis Plan

6.2.1 General Methodology

For baseline demographics and subject characteristics, continuous measures will be summarized as mean, standard deviation, median, minimum and maximum. Categorical data will be summarized as frequencies and percentages for each data category. As appropriate, characteristics of affected segments may be similarly summarized.

For segment specific efficacy endpoints of interest, the analysis unit will be treated segment as opposed to subject. That is, assuming no missing data, subjects with bilateral DVTs will have two segments for analysis. Efficacy results will be summarized for the Efficacy Segment Set at each measurement time point. For changes from baseline at follow-up time points, continuous measures will be summarized as mean, standard deviation, median, minimum, maximum. Categorical outcomes will be summarized in two-way tables. All statistical analyses will take into account the repeated measures nature of multiple segments per subject. With subject as a random effect, the SAS GLIMMIX procedure will generally be used to evaluate the statistical significance for changes from baseline.

Analysis for subject specific efficacy measures such as SF-36 will be performed on the Evaluable Subject Set with subject as the analysis unit. Statistical significance for changes from baseline will be assessed by t-test or a nonparametric test appropriate for the data distribution.

Further analysis details will be described in the Statistical Analysis Plan.

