6.2.2 Efficacy

Efficacy analyses will be performed on the Efficacy Segment Set or Efficacy Subject Set as appropriate for the nature of the data.

Primary Clinical Efficacy Analysis:

The 30 day Villalta score change from Baseline will be analyzed as a binary variable for a segment's status as having achieved a ≥ 4 point reduction or not. Study success will be defined by $\geq 50\%$ of the efficacy evaluable segments achieving at least a 4 point reduction. In addition, as a continuous measure, change in Villalta score from Baseline to 30 day Post-EkoSonic® Treatment will also be summarized and analyzed as described above in 6.2.1 General Methodology.

Primary Technical Efficacy Analysis:

The change in blood flow calculated by time to washout in the affected segment from Baseline and Post-EkoSonic® Treatment will be analyzed as a continuous measure. A statistically significant (2-sided $p < 0.05$) improvement in flow rate, i.e. reduction in time to washout, will be considered a success for the study.

Secondary Efficacy Analyses:

For all secondary efficacy endpoints described in Section 3.2.1, i.e. VVI score change from Pre- EkoSonic® Treatment to Post-Treatment, Villalta score change from Baseline to 90, 180, and 365 days, re-occlusion rate up to 365 days, change from Baseline to all follow-up time points for SF-36 QOL and PCS component scores, CEAP classification, and VCSS, occurrences of symptomatic PTS-induced admission to emergency room or unplanned visit

to physician office or hospitalization from post EkoSonic® Treatment up to 365 days thereafter, time from starting initial thrombolytic infusion to discharge from hospital, analyses will be performed as described above in 6.2.1 General Methodology. For symptomatic PTS-induced healthcare utilization, time to event analyses will be performed for days from EkoSonic® Treatment to first occurrence for each of (a) admission to emergency room, (b) unplanned visit to physician office, and (c) hospitalization.

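### A day-30 Villalta score is required for every efficacy analysis, so treated limbs and subjects are dropped from endpoints that do not use that score

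*Protocol*

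**What the plan says.** Section 6.1 sets two conditions for an efficacy evaluable segment: "a) were successfully crossed and received EkoSonic® Treatment, and (b) had Villalta scores available at both Baseline and 30 days Post-EkoSonic® Treatment visit". The resulting Efficacy Segment Set "includes all efficacy evaluable segments and will be used for all segment specific efficacy analyses".

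The subject-level set follows the same pattern. It takes "enrolled subjects for whom at least one affected segment" meets both conditions, and it "includes all efficacy evaluable subjects and will be used for all subject specific efficacy analyses such as for quality of life measures".

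The analysis sections repeat the rule. Section 6.2.1: "Efficacy results will be summarized for the Efficacy Segment Set at each measurement time point". Section 6.2.2: "Efficacy analyses will be performed on the Efficacy Segment Set or Efficacy Subject Set as appropriate for the nature of the data". The only other set in section 6.1 is for safety.

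Section 6.1 also says that missing data are not imputed in the primary analyses and that sensitivity analyses for missing data may be done. The protocol uses segment and limb interchangeably (synopsis, sections 3.1.1 and 6.1), and so does this note.

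**The concern.** The day-30 Villalta score is a natural requirement for one outcome, the change in Villalta score at day 30. The protocol makes it the entry ticket to all efficacy outcomes, several of which are measured before day 30 or do not involve the Villalta scale.

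Two things follow. Valid data are discarded, including data for a primary endpoint with its own success criterion. Inclusion in those analyses also depends on a later measurement unrelated to the outcome. This is least comfortable for time to first PTS-induced visit. That clock starts at treatment, yet only subjects with a treated limb scored at a visit whose window opens on day 23 (30 minus 7) are counted. A treated subject who withdraws or dies before that visit does not contribute, and neither does any PTS-induced visit that the subject had first.

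**Working it through.** **Step 1: what each endpoint needs, against what the set demands.**

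| Endpoint (protocol section) | Data it needs | Uses day-30 Villalta? | Set imposed |
|---|---|---|---|
| Villalta response at day 30 (3.1.1) | Baseline and day-30 score | Yes | Efficacy Segment Set |
| Time to washout (3.1.2, primary technical) | Baseline and post-procedure measurement | No | Efficacy Segment Set |
| VVI (3.2.1, item 1) | Baseline and post-procedure measurement | No | Efficacy Segment Set |
| Villalta at 90, 180, 365 days (3.2.1, item 2) | Baseline and that visit's score | No | Efficacy Segment Set |
| Re-occlusion at 365 days (3.2.1, item 3) | Follow-up duplex | No | Efficacy Segment Set |
| PTS-induced visits (3.2.1, item 5; 6.2.2) | Dates from treatment onward | No | Efficacy Subject Set |
| Time to discharge (3.2.1, item 6) | Start of infusion and discharge | No | Efficacy Subject Set |

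Sections 3.1.2 and 3.2.1 do not name the imaging method for washout or VVI. That does not matter here: post-treatment venography follows the procedure immediately and duplex is due within 24 hours (section 4.2.4), both well before day 30.

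**Step 2: is there a way out in the text?** Section 6.2.2 lets the analyst choose between two sets, but both carry the day-30 condition. The sensitivity analyses in section 6.1 are optional, name no all-treated set and leave the main sets as they are.

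**Step 3: bilateral subjects.** Limbs are treated at least 30 days apart and evaluated separately through day 90 (section 4.2.1). If one treated limb is scored and the other is not, the subject stays in the Efficacy Subject Set, but the unscored limb leaves every segment-level analysis.

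**Step 4: the plan's own figure.** Section 6.2.4 states a probability of 0.83 of observing at least 50% successes in 70 independent segments when the true rate is 55%. The exact binomial probability of 35 or more out of 70 at 0.55 is 0.832, so the figure reproduces. It concerns the primary clinical endpoint, which this point does not affect. Only the 70 is used below, as a scale.

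**Step 5: size.** The protocol gives no rate of missing day-30 scores. Let m be the share of treated limbs without one, with m = 5%, 10% and 15% as assumptions. Treated limbs behind 70 evaluable limbs = 70/(1 − m). Standard error with the restricted set relative to all treated limbs = √(1/(1 − m)), assuming independent limbs and equal variance.

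| m (assumed) | Treated limbs | Excluded, at most | Standard error ratio |
|---|---|---|---|
| 5% | 70/0.95 = 73.7 | 3.7 | 1.026 |
| 10% | 70/0.90 = 77.8 | 7.8 | 1.054 |
| 15% | 70/0.85 = 82.4 | 12.4 | 1.085 |

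These are upper bounds, because they suppose that every unscored limb has the other endpoint's data. That is plausible for washout and VVI. For 365-day duplex and later Villalta scores, some of these limbs will belong to subjects who withdrew and have no later data under any definition.

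**Step 6: possible shift.** If unscored limbs differ from scored ones by d percentage points in 365-day re-occlusion (d = 10 to 20, assumed), the reported rate differs from the all-treated rate by m × d. That runs from 0.05 × 10 = 0.5 to 0.15 × 20 = 3.0 points, again an upper bound on what could be recovered. Nothing in the protocol says in which direction.

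**The case against.** The best defence is that a single evaluable cohort gives constant denominators, which is a recognisable choice in a single-arm study of a cleared device. Enrollment is also counted in evaluable subjects (section 4.0), so the planned analysable number is not reduced; the loss is relative to all treated limbs. Further details are left to an SAP that was not available here. Villalta is scheduled at early termination, and how such a score is used is properly an SAP matter. All of this limits the size. It does not remove the point, because the protocol itself fixes the set for all efficacy analyses and an SAP that follows it inherits the rule.

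A reader might go further in four ways that the document does not support.

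- *Early deaths and serious events disappear from the trial.* They do not. Section 6.2.3 reports deaths and SAEs in the Safety Subject Set, which has no Villalta condition, and hospitalization counts as serious under section 5.3. Only the efficacy time-to-event analysis loses these subjects. Events before day 23 in retained subjects are still counted there.
- *The rule contradicts section 4.5, under which data collected before withdrawal stay in the study.* That sentence is about keeping data. It does not decide membership of an analysis set.
- *The washout test loses a definite amount of power.* The protocol states no power for washout, so no loss can be calculated from it.
- *The primary clinical result is compromised, for example through revascularized limbs.* Section 6.1 says "A treated segment that received a revascularization procedure within 30 days Post-EkoSonic® Treatment will be regarded as a failure for the primary efficacy endpoint", while section 6.2.2 counts the proportion "of the efficacy evaluable segments achieving at least a 4 point reduction". A revascularized limb without a day-30 score is therefore not clearly placed. That is a separate question. Section 4.6 keeps such subjects at all planned visits, so the case should be uncommon. Settling it could alter the primary denominator after the interim look described in section 6.2.5, so it does not belong with this change.

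**Conclusion.** The point holds. As written, the protocol excludes treated limbs from washout, VVI, 365-day re-occlusion and the 90-, 180- and 365-day Villalta analyses for want of a score that none of these uses. It likewise excludes subjects with no scored treated limb from time to discharge and from time to PTS-induced visits. This is a rule wrongly fixed in the protocol, not detail left to an SAP.

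The effect is modest: at most about 4 to 12 limbs per 70 evaluable, and standard errors up to about 3% to 9% larger for the peri-procedural endpoints, with less to recover at later visits. These figures rest on an assumed 5% to 15% of treated limbs without a day-30 score, on independent limbs, and on the other endpoint's data being present. The direction of any bias cannot be told from the document. The change should be made, but the primary clinical conclusion does not depend on it.

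**What to change.** Restrict the day-30 Villalta condition to the day-30 Villalta analyses, and define the remaining sets by endpoint:

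- Washout and VVI: all treated segments with that endpoint's pre- and post-procedure measurements.
- Re-occlusion: all treated segments with the follow-up duplex.
- Villalta at 90, 180 and 365 days: all treated segments with Baseline and that visit's score. The other visit-based scales can follow the same principle.
- Time to discharge and PTS-induced visits: all treated subjects, with the time-to-event analysis censored at last contact.

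The cost is a change of wording in sections 6.1 to 6.2.2. The measurements are already scheduled, so no new data collection is needed. The drawback is that denominators will differ between endpoints and must be shown in each table. The denominator of the primary clinical endpoint does not change.

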APPENDIX I: VEINES QOL

APPENDIX J: Adherence to Conservative Treatment Form

A. PROTOCOL SYNOPSIS

Title:	ACCelerated ThrombolySiS for Post-Thrombotic Syndrome Using the EKOS System (ACCESS PTS)
Design:	A prospective, single arm, multi-center study
Brief Device Description:	The EkoSonic® Endovascular System employs high frequency (2-3MHz), low power ultrasound to facilitate the delivery of therapeutic agents to the intravascular treatment site in the peripheral vasculature.
Purpose:	To evaluate the efficacy of ultrasound accelerated thrombolysis using the EkoSonic® Endovascular System with standard infusion of thrombolytic drug for post-thrombotic syndrome and chronic venous occlusion.
Primary Endpoint:	Clinical effectiveness will be evaluated using the Villalta score at Baseline compared to 30 days Post-EkoSonic® Study Treatment Procedure (EkoSonic® Treatment). Success will be defined by 50% of the subjects achieving at least a 4 point reduction in the Villalta score.
Population:	Subjects with lower extremity deep vein thrombosis (who have failed conservative treatment) objectively diagnosed with imaging \geq 6 months; prior persistent DVT at enrollment evaluation; Villalta score \geq 8. Subjects must be \geq 18 years of age and \leq 75 years of age.
Enrollment:	Up to 200 efficacy evaluable subjects, some with bilateral DVTs. Efficacy evaluable DVT limbs are those (1) with Villalta scores available at both Baseline and 30 days Post-EkoSonic® Treatment and (2) the clot in the affected segment was successfully crossed and received EkoSonic® Treatment.
Clinical Site Locations:	Up to 30 centers within the United States.
Time Course:	Enrollment period of up to 12 months with 365 day follow-up. Subject participation is approximately 12 months.

B. STUDY FLOWCHART and SCHEDULE OF EVENTS

ACCESS PTS Schedule of Assessments	Visit 1 (Within 30 days of treatment) Screening/Baseline	Visit 2 Day 0 Pre-EkoSonic® Treatment	Visit 2 Day 0 Post-EkoSonic® Treatment	Discharge	Visit 3 Day 30 ± 7 days	Visit 4 Day 90 ± 10 days	Visit 5 Day 180 ± 14 days	Visit 6 Day 365 ± 14 days	Early Termination
ACTION									
Informed Consent	X								
Demographics	X								
Medical History & Risk Factors	X								
Inclusions/Exclusion Criteria	X								
Pregnancy test	X								
Physical Exam	X								
Duplex Ultrasound	X ¹		X ²		X	X	X	X	X
Adherence to Conservative Therapy Form	X								
Laboratory Tests	X ³	X ⁴	X ²						
Villalta Scale	X				X	X	X	X	X
CEAP Classification	X				X	X	X	X	X

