4.2.6 Follow-Up Visits and Early Termination

At each of the follow-up visits: **Days 30± 7 days, 90± 10 days, 180± 14 days, 365 ± 14 days and at early termination**, the following assessments shall be performed:

- Duplex imaging
- Villalta scale (both legs)
- CEAP classification(both legs)
- VCSS (both legs)
- SF-36
- VEINES-QOL
- Leg circumference (both legs)
- Review of compliance with anticoagulant therapy, ECS, and exercise
- Serious Adverse and bleeding events
- Concomitant medications

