4.6 Revascularization

If, at any time during the follow-up period a subject is found to have re-occlusion of a venous segment that is associated with escalation of symptoms, the subject may undergo revascularization using any method the treating physician feels is appropriate. The subject shall remain in the study and shall attend all planned follow-up visits. All revascularization procedures shall be documented on the revascularization case report form.

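### The re-treatment failure rule in Section 6.1 stops at 30 days, but the primary Villalta score may be taken up to Day 37, so re-treatment in between is not clearly a failure

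*Protocol*

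**What the plan says.** **Failure rule.** Protocol Section 6.1: "A treated segment that received a revascularization procedure within 30 days Post-EkoSonic® Treatment will be regarded as a failure for the primary efficacy endpoint". The sentence then explains that such a segment is counted as not having reached the 4-point reduction.

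**Evaluability.** The same section keeps a segment in the Efficacy Segment Set if it was crossed and treated and "had Villalta scores available at both Baseline and 30 days Post-EkoSonic® Treatment visit". Later revascularization does not remove it.

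**Timing of the score.** The Schedule of Events heads the column "Visit 3 Day 30 ± 7 days". Section 4.2.6 gives the same window in its list of visits: "Days 30± 7 days, 90± 10 days, 180± 14 days, 365 ± 14 days and at early termination".

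**Re-treatment.** Section 4.6: "If, at any time during the follow-up period a subject is found to have re-occlusion of a venous segment" with escalating symptoms, "the subject may undergo revascularization using any method the treating physician feels is appropriate". It continues: "The subject shall remain in the study and shall attend all planned follow-up visits".

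**Primary analysis.** Section 6.2.2: "The 30 day Villalta score change from Baseline will be analyzed as a binary variable for a segment's status" as a responder or not. The study succeeds if at least 50% of evaluable segments respond.

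**The concern.** The failure rule counts days from treatment, while the score it protects is tied to a visit with a window. The two end points can differ by up to a week. If re-treatment falls after Day 30 but before a late visit, Section 4.6 keeps the subject in follow-up, Section 6.1 keeps the segment evaluable, and nothing in the literal rule makes it a failure. The responder status is then read from a score that reflects the second procedure as well as the study treatment.

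Section 4.6 ties re-treatment to symptomatic re-occlusion, so these limbs are among those least likely to have responded to the study treatment alone. Study success is a bare comparison of the observed proportion with 50%, so each limb's classification enters the verdict directly.

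**Working it through.** **1. The days involved.** The visit window runs from Day 30 − 7 = Day 23 to Day 30 + 7 = Day 37. The literal rule covers re-treatment through Day 30. For re-treatment to fall outside the rule and on a day before the score, it must occur on Days 31-36, with the visit later but no later than Day 37.

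**2. Four cases under the two readings and under the rule proposed below.**

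| Re-treated | Scored | Rule ends at 30 days | Rule ends at the 30-day visit | Proposed rule |
|---|---|---|---|---|
| Day 20 | Day 30 | failure | failure | failure |
| Day 29 | Day 23 | failure | by score | failure |
| Day 33 | Day 37 | **by score** | failure | failure |
| Day 45 | Day 30 | by score | by score | by score |

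The readings disagree in the second and third rows. Only in the third can a score taken after re-treatment count as a success.

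**3. Direction.** In the third row the limb is either a failure (visit reading) or a failure or success according to its score (literal reading). The literal reading can therefore raise the success count for such limbs and can never lower it.

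**4. The plan's own figures.** Section 6.2.4 uses 70 independent segments, so success needs 35 or more. Exact binomial tail probabilities P(X ≥ 35 | n = 70, p):
- p = 0.55: 0.832 (stated 0.83)
- p = 0.39: 0.040 (stated ≤0.04)

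Both reproduce and are not in dispute.

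**5. Size per limb.** 1/70 = 1.4 percentage points. At the enrolment ceiling of 200 evaluable subjects, with at least one segment each, it is at most 1/200 = 0.5 points.

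**6. Outer bound.** The protocol gives no rate of revascularization on Days 31-36, so the number k of affected limbs out of 70 is an assumption. With the other 70 − k limbs responding independently with probability p:
- all k counted as failures: P(Bin(70 − k, p) ≥ 35)
- all k counted as successes: P(Bin(70 − k, p) ≥ 35 − k)

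| k | p = 0.39: failures / successes | p = 0.55: failures / successes |
|---|---|---|
| 0 | 0.040 / 0.040 | 0.832 / 0.832 |
| 1 | 0.032 / 0.053 | 0.798 / 0.859 |
| 2 | 0.025 / 0.070 | 0.761 / 0.884 |
| 3 | 0.019 / 0.090 | 0.719 / 0.905 |

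The second figure in each pair assumes that every affected limb improves by 4 points. It is a bound, not an estimate.

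**The case against.** **The visit reading.** The protocol uses 30 days after treatment as the name of the primary time point, and the Section 6.1 sentence itself uses the phrase again for the score. On that reading the rule already covers re-treatment up to the visit. This is a fair reading and it stands as one of two. It does not settle the matter, because the evaluability criterion in the same section adds the word visit and the failure rule does not.

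**Detail for the statistical analysis plan.** Section 6.2.1 defers further detail to a plan that is not shown, and that plan may match re-treatment dates to assessment dates. This also stands. But the protocol set the cut-off itself, so the point concerns a stated rule that does not fit its own visit window, not a missing rule.

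**Rarity.** A false success needs symptomatic re-occlusion, re-treatment on Days 31-36, a visit not yet done but then held by Day 37, and a 4-point gain over baseline within at most six days of a repeat procedure. Section 4.2.5 itself anticipates limb swelling and discomfort around discharge. This objection largely stands and limits the weight of the point.

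**Stronger readings that the protocol does not support.**
- A reader might infer that the rule is also wrong in the other direction, because a limb scored on Day 23 and re-treated on Day 29 is failed on the literal reading. Requiring freedom from re-treatment through Day 30 is a legitimate, conservative composite definition, not an error.
- A reader might infer that the gap could decide the trial, since one limb separates 34/70 (48.6%) from 35/70 (50.0%). That is a chosen knife-edge which would apply to any single-limb question.
- A reader might infer that the chance of a false study success is materially raised. The bound above shows only what certain success in every affected limb would do.

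**Conclusion.** The point holds in a limited form. Read literally, the rule lets a limb re-treated on Days 31-36 count as a primary success on a score taken after re-treatment. Read as ending at the visit, it does not. The protocol does not say which is meant, so the primary endpoint is ambiguous for these limbs.

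Where the gap applies it can only favour success, by at most 1.4 percentage points per limb at 70 segments and about 0.5 at 200. The number of such limbs is unknown and probably near zero; with none, nothing changes. That the wording leaves the case open is clear from the text. That the literal reading is the intended one is not established.

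**What to change.** Reword the sentence in Section 6.1 so that a treated segment revascularized by Day 30, or before its Day-30 (±7) Villalta assessment, whichever is later, is a failure for the primary clinical efficacy endpoint. This fails a limb under either reading of the present text, so it keeps the conservative treatment of limbs scored early and re-treated by Day 30, and it cannot raise the success rate under either reading. Apply it to all evaluable segments, including those already counted at the interim futility analysis.

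The cost is one sentence. Section 4.6 already requires every revascularization to be recorded on its own case report form (assumed to carry the date), and no visit, treatment or clinical rule changes. The downside is that the observed success rate may fall slightly.
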